Hypothesis of this phase II study is that ixazomib and lenalidomide as maintenance therapy after autologous PBSC transplant for Multiple Myeloma will be safe and tolerable and prolong the time to disease progression post transplant. The treatment regimen is alternating ixazomib with lenalidomide every two months until disease progression, intolerable toxicity or maximum of 24 months of therapy. The dose of ixazomib is 4.0 mg po on days 1, 8 and 15 per each 28-day cycle given for two consecutive months, followed by then lenalidomide 10 mg po daily for two consecutive months, then ixazomib for two months etc. Dose reduction for toxicity will be incorporated. If >30 days off initially planned next cycle of therapy, then patient will be taken off study. Toxicity will be graded per CTCAE version 4.0. The first four months of therapy will be used as the time period to evaluate end point of toxicity for stopping rules. Toxicity that meets stopping rules will be determined based on the number of patients that are withdrawn from study for significant toxicity (grade IV, non-hematological, non-metabolic, non-peripheral neuropathy) and the number of patients who stop therapy for toxicity and are withdrawn from study as they could not recover adequately and resume therapy by 30 days from the initial stopping of the study drugs. We shall consider the withdrawal rate to be excessive, and hence the therapy to be too toxic, if the true withdrawal rate from the study exceeds 15% in the first four months. An interim analysis at 15 treated patients will be conducted. If > 50% of patients are unable to receive > 50% of planned therapy in first 12 months of treatment, the study will be terminated due to lack of feasibility. Another endpoint is time to disease progression. Patients will be followed for initial response and for progression of disease, response criteria will be determined by International Myeloma working group criteria. In patients with chemo-refractory disease at the time of ASCT, the therapy will be felt to be promising if median time to progression is >9 months. If chemo-sensitive disease at time of ASCT, the therapy will be felt to be promising if median time to progression is >41 months based on CALGB 10014 lenalidomide maintenance study post ASCT. Cytogenetic information will be collected and initial response rates and outcome will be descriptively reported. Patients will be followed for overall survival. The incidence of secondary cancers will also be collected. If this study regimen is deemed to be potentially efficacious and is not regarded as too toxic per stopping rules outlined above and observed EFS rate are consistent with rates that match or exceed historical benchmarks, then a phase III trial to show efficacy rate of this regimen over single agent therapy will be designed.

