4. STUDY DESIGN

4.1 Overview of Study Design

Treatment regimen

Alternating ixazomib 4.0 mg po on days 1, 8 and 15 per each 28- day cycle for two consecutive cycles, followed by then lenalidomide 10 mg po daily for two consecutive cycles until disease progression, intolerable toxicity or maximum of 24 cycles of therapy. Dose reduction for toxicity will be incorporated. If >30 days off initially planned next cycle of therapy, then patient will be taken off study. Toxicity will be graded per CTCAE version 4.0.

Therapy will start 30-120 days post autologous transplant when the patient is recovered from acute toxicity. See study flow chart on page 4 for scheduling of events for study.

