New or worsening Grade 4 peripheral neuropathy	Discontinue ixazomib	
Grade 2 Rash	Symptomatic recommendations as per section 6.10	At the discretion of the investigator, may require dose modification.
Grade 3 Nonhematologic, nonperipheral neuropathy toxicity judged to be related to ixazomib	Hold ixazomib until resolution to Grade < 1 or baseline	Symptomatic recommendations noted in Section 6.10
If not recovered to < Grade 1 or baseline within 30 days	Reduce ixazomib to next lower dose upon return to < Grade 1 or baseline	
Subsequent recurrence Grade 3 that does not recover to < Grade 1 or baseline within 30 days	Hold ixazomib until resolution to Grade < 1 or baseline	
Grade 4 Nonhematologic nonperipheral neuropathy toxicities judged to be related to ixazomib	Consider permanently discontinuing ixazomib	Exceptions are cases in which the investigator determines the patient is obtaining a clinical benefit

Once ixazomib is reduced for any toxicity, the dose may not be re-escalated.

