Rash Grade 2	Symptomatic recommendations as per Section 6.10	At the discretion of the investigator, may require dose modification.	
Grade 3 nonhematologic, nonperipheral neuropathy toxicity judged to be related to lenalidomide	Hold study drug until resolution to Grade < 1 or baseline	Symptomatic recommendations noted in Section 6.7	
If not recovered to $<$ Grade 1 or baseline within 30 days	Reduce study drug 1 to next lower dose upon return to $<$ Grade 1 or baseline		
Subsequent recurrence Grade 3 that does not recover to $<$ Grade 1 or baseline within 30 days	Hold study drug until resolution to Grade < 1 or baseline Reduce study drug to next lower dose	Monitor closely, take appropriate medical precautions, and provide appropriate symptomatic care	
Grade 4 nonhematologic, nonperipheral neuropathy toxicities judged to be related to lenalidomide	Consider permanently discontinuing lenalidomide	Exceptions are cases in which the investigator determines the patient is obtaining a clinical benefit	

**Fred Hutchinson Cancer Research Center
Clinical Study Protocol [FHCRC 9266]**

Once lenalidomide is reduced for any toxicity, the dose may not be re-escalated.

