6.15 Termination of Treatment and/or Study Participation

Patients will be informed that they have the right to withdraw from the study at any time for any reason, without prejudice to their medical care. The investigator also has the right to withdraw patients from the study for any of the following reasons:

- Adverse event
- Protocol violation
- Lost to follow-up
- Progressive disease
- Study terminated
- The treatment appears detrimental in the judgment of primary physician

**Fred Hutchinson Cancer Research Center
Clinical Study Protocol [FHCRC 9266]**

- They develop non-hematological, non-metabolic, non-peripheral neuropathy grade IV toxicity
- They are unable to resume therapy more than 30 days after initial stopping of therapy for toxicity or cannot tolerate lowest dose reduction level
- Repeated noncompliance to protocol in view of principal investigator

Patients who are withdrawn from the study will not be replaced.

At the time of withdrawal, all study procedures outlined for the End of Study visit should be completed per study calendar (See Study Flow Chart). The primary reason for patient's withdrawal from the study should be recorded in the source documents and CRF.

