7.1.7 Safety Analysis

The first endpoint is to evaluate the toxicity of the proposed therapy. The first four months of therapy will be used as the time period in which toxicity will be evaluated and stopping rules for unacceptable toxicity will be implemented. Rules for stopping therapy will be based on rate of withdrawal due to significant toxicity (grade IV, non-hematological, non-metabolic and non-peripheral neuropathy). A true withdrawal rate within first 4 months of 15% will be considered excessive. Withdrawal rate will be assessed after every ten patients are treated. Enrollment will not be held though until the 10th patient enrolled becomes evaluable. Sufficient evidence will be taken for a lower limit to the corresponding one sided 80% confidence interval that exceeds 15%. Operationally observed rates that say regimen is too toxic would be 2/5, 3/10, 4/15, 5/20, 6/25 and 7/30. If the true probability of withdrawal from the study is 5%, the probability of deeming this regimen as too toxic after 15 or 30 patients have been treated is approximately .03 and .03, respectively. If the true probability of withdrawal is 10%, these probabilities are approximately .13 and .15, respectively. On the other hand, if the true probability of withdrawal is .30, then the probability of judging this regimen as too toxic after 15 or 30 patients is approximately .78 and .91, respectively.

With the semi-continuous monitoring of the withdrawal rate, the estimate of this rate, should the study run to completion, will be biased slightly downward. Without consideration of this bias, 30 patients will allow us 80% confidence that the estimated withdrawal rate will be within approximately .094 of the true rate under the assumption that the true rate is 20%. The incidence of second cancers will also be collected.

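### A patient who permanently loses one of the two drugs to toxicity in the first four months may be scored in neither version of the stopping rule, depending on which section is followed

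*Combined protocol and SAP*

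**What the plan says.** The counted event has two versions, and both require withdrawal from the study.

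- Section 7.1.7: "Rules for stopping therapy will be based on rate of withdrawal due to significant toxicity", which it limits to Grade IV events outside the hematological, metabolic and peripheral neuropathy classes. There is no other component.
- Protocol Summary, Overview of Study Design: first, "patients that are withdrawn from study for significant toxicity (grade IV, non-hematological, non-metabolic, non-peripheral neuropathy"; second, patients who stopped for toxicity and were withdrawn because "they could not recover adequately and resume therapy by 30 days from the initial stopping of the study drugs". The second component has no grade limit and no neuropathy exclusion.

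The dose tables in section 6.4 act drug by drug. In Table 6-1 the step below 2.3 mg of ixazomib is discontinuation. Tables 6-3 and 6.5 end the drug in question for new or worsening Grade 4 neuropathy. For other related Grade 4 non-hematologic toxicity they say "Consider permanently discontinuing ixazomib" and "Consider permanently discontinuing lenalidomide", with an exception where the investigator sees clinical benefit.

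Section 6.15 lists reasons for which the investigator has the right to withdraw a patient from the study. They include Grade IV toxicity outside the hematological, metabolic and neuropathy classes, and: "They are unable to resume therapy more than 30 days after initial stopping of therapy for toxicity or cannot tolerate lowest dose reduction level". Section 4.1 runs a different 30-day clock: "If >30 days off initially planned next cycle of therapy, then patient will be taken off study".

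**The concern.** Toxicity is the only primary endpoint (section 3.1), the regimen under test is the alternation, and passing the toxicity rule is one condition for designing a phase III trial (section 7.1.8). A patient who can no longer alternate because of toxicity is a failure one would expect the rule to consider. As written, the same toxicity can be an event or a non-event according to whether the site follows the dose tables or section 6.15. The alternation itself opens the gap, because starting the other drug on schedule can be read as resuming therapy.

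Section 7.1.7 acknowledges a slight downward bias from repeated monitoring. This is a separate source of downward bias, and the plan does not mention it. With boundaries as low as 2/5 and 3/10, one patient's classification can decide a look.

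**Working it through.** **1. How each case is scored on a literal reading**

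| Case in the first four months | 7.1.7 | Summary |
|---|---|---|
| Grade IV in the counted class, patient withdrawn from the study | counted | counted |
| Same toxicity, one drug stopped, patient kept on the other | not counted | not counted |
| Grade 4 neuropathy ends one drug, other drug started within 30 days | not counted | not counted |
| Grade 4 neuropathy, not resumed by 30 days and withdrawn | not counted | counted |
| Lowest-dose intolerance below Grade IV, recovered within 30 days | not counted | not counted |
| Same, not resumed by 30 days and withdrawn | not counted | counted |

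The fifth row holds even if the patient is withdrawn under 6.15 for that reason, because neither version of the event names it.

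**2. Timing with 28-day cycles**

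Cycle k starts on day 28(k − 1) + 1. Cycle 2 is therefore days 29–56, cycle 3 starts on day 57, cycle 5 starts on day 113, and four cycles end on day 112.

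- Ixazomib ended on or after day 29: lenalidomide is due on day 57, at most 57 − 29 = 28 days later. Neither 30-day clock is exceeded if it starts on time. The next ixazomib cycle that cannot be given is cycle 5, so the section 4.1 limit is reached at 113 + 30 = day 143, after the window.
- Ixazomib stopped on day 1, 8 or 15 of cycle 1: day 57 is 56, 49 or 42 days later. The clock from initial stopping (Summary, 6.15) is exceeded. The clock from the planned next cycle (4.1) is not, since 57 − 29 = 28.
- Lenalidomide stopped by day 82 in cycle 3: 113 − 82 = 31 days, which exceeds the clock from initial stopping. A stop in cycle 4 (day 85 onward) gives at most 113 − 85 = 28 days and does not.

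**3. The plan's own probabilities**

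Inputs from 7.1.7: boundaries 2/5, 3/10, 4/15, 5/20, 6/25 and 7/30. With event probability p, let f_n(x) be the probability of x events in n patients without having stopped:

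f_n(x) = (1 − p) f_{n−1}(x) + p f_{n−1}(x − 1).

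At each look, the mass at or above the boundary is removed and added to the stopping probability.

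| p | Stated, by 15 / 30 | Looks every 5 | Looks every 10 |
|---|---|---|---|
| .05 | .03 / .03 | .030 / .031 | .012 / .013 |
| .10 | .13 / .15 | .129 / .146 | .070 / .096 |
| .30 | .78 / .91 | .775 / .912 | .617 / .892 |

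The stated figures reproduce with looks every five patients. The text says every ten, so both are carried forward.

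**4. Effect of unscored failures**

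If the true toxicity-failure rate is t and u percentage points of it go unscored, the rule sees p = t − u. The documents give no value for u; those below are assumptions. Entries are P(stop by 30) with looks every five patients (every ten in brackets).

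| t | u = 0 | u = 5 | u = 10 |
|---|---|---|---|
| 15% | .354 (.285) | .146 (.096) | .031 (.013) |
| 20% | .594 (.532) | .354 (.285) | .146 (.096) |
| 30% | .912 (.892) | .790 (.751) | .594 (.532) |

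**The case against.** A reader might infer that every patient who loses one drug escapes both versions, or that Grade 4 neuropathy is excluded from both. The documents do not support either reading. The Summary's second component counts any toxicity, neuropathy included, if the patient fails to resume by 30 days and is withdrawn. A Grade IV toxicity in the counted class is scored in both versions once the patient is withdrawn. Stops in cycle 1, or by day 82 in cycle 3, exceed the clock from initial stopping.

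Nor is a lenalidomide start on day 57 automatic. Section 6.4.2 requires neuropathy and other non-hematologic toxicity to have resolved to Grade 1 or baseline, and exclusion criterion 14 keeps baseline neuropathy below Grade 2. A patient still unrecovered at 57 + 30 = day 87 comes off study under 4.1, inside the window, and is a Summary event. All of this narrows the gap to patients who recover in time and go on to the other drug, or who are kept on study under the dose tables. It does not close the gap.

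The frequency may be low. Two or more dose reductions were needed in 8–20% of patients in C16003, C16004, C16005, C16006 and C16008, and a reader might take this as evidence for a rate. It is not. Those studies include twice-weekly dosing and doses above the MTD, C16005 counts reductions of any drug in the combination, and the figures cover whole treatment courses. In C16013 no patient needed more than one reduction, and in TB-MC010034 1 of 14 did. Here only two ixazomib cycles (six doses) fall in the window, and reaching discontinuation in Table 6-1 takes a third step down.

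It is also fair to say that these patients still appear in the adverse event data, that delivery of planned therapy is a secondary objective, and that 7.1.8 has a feasibility rule. That rule, however, needs more than half of patients to fall short over 12 months and does not measure toxicity. Finally, the plan deliberately excludes hematologic, metabolic and neuropathy toxicity from its significant-toxicity class, so counting every one-drug stop would change the endpoint. That point stands and shapes the fix.

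**Conclusion.** The concern holds in limited form. The dose tables, section 6.15 and the two event definitions do not give one status to a patient who has permanently stopped one drug for toxicity, so such a patient may be scored in neither version of the rule. Under 7.1.7, Grade 4 neuropathy and lowest-dose intolerance below Grade IV are never counted. Under the Summary they count only after failure to resume by 30 days and withdrawal. Where the patient is unscored, the bias in the monitored rate is downward.

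Its size cannot be established from the documents. At a true failure rate of 20%, leaving 5 points unscored would lower the chance of stopping by 30 patients from .59 to .35, and leaving 10 points unscored would lower it to .15 (.53, .29 and .10 with ten-patient looks). These figures rest on the assumed unscored share, independent patients, and every patient being evaluable at each look. The rule's own arithmetic is not in question. The passages should be reconciled because they decide what counts on the primary endpoint.

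**What to change.** 1. Reconcile Tables 6-1, 6-3 and 6.5 with sections 4.1, 6.15 and 7.1.7 and the Summary, so that a patient who has lost one drug has the same status throughout, on one 30-day clock. Which clinical rule applies is for the sponsor to choose.
2. Use one event definition in 7.1.7 and the Summary. It should score a toxicity that leads to permanent discontinuation of either study drug within the first four months, whether or not the patient stays on the other drug.
3. State whether the present hematologic, metabolic and neuropathy exclusions apply to that event, and confirm that 15% is still the right limit for it. If the limit is kept, the listed boundaries can stay.

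Cost: mainly protocol wording. Section 6.15 records only the primary reason for withdrawal from the study, so a reason and date of discontinuation for each drug may need a case report form field. The monitored rate and the chance of stopping would rise by an amount that depends on how often one-drug stops occur. The rise need not be small: if 5 points are now missed at a true 20%, it is from .35 to .59 with five-patient looks.

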7.1.1 Determination of Sample Size

Thirty Multiple Myeloma patients post ASCT are to be enrolled over 2-3 years. Expect to enroll 1-1.5 patients per month.

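### The toxicity stopping rule schedules looks every ten patients, but its boundaries and all six quoted stopping probabilities belong to looks every five

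*Combined protocol and SAP*

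**What the plan says.** Section 7.1.7 sets out the rule in one paragraph.

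- Threshold: "A true withdrawal rate within first 4 months of 15% will be considered excessive".
- Schedule: "Withdrawal rate will be assessed after every ten patients are treated".
- Criterion for stopping: "Sufficient evidence will be taken for a lower limit to the corresponding one sided 80% confidence interval that exceeds 15" per cent.
- Boundaries: "Operationally observed rates that say regimen is too toxic would be 2/5, 3/10, 4/15, 5/20, 6/25 and 7/30".
- Stopping probabilities at a true rate of 5%: "the probability of deeming this regimen as too toxic after 15 or 30 patients have been treated is approximately .03 and .03, respectively".
- At 10%: "If the true probability of withdrawal is 10%, these probabilities are approximately .13 and .15, respectively".
- At 30%: "the probability of judging this regimen as too toxic after 15 or 30 patients is approximately .78 and .91, respectively".

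The paragraph also says that enrolment continues while the tenth patient is being evaluated, and it calls the monitoring semi-continuous. Section 7.1.8 plans an analysis at 15 treated patients, but that one concerns feasibility (how much planned therapy was received), not withdrawal for toxicity.

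**The concern.** A schedule of every ten patients has three looks. The boundary list has six, and half of them (5, 15 and 25) fall where the schedule has no look. Probabilities are also quoted at 15 patients, again not a look. So the stated schedule and the stated operating characteristics may describe different rules.

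Toxicity is the sole primary endpoint (Section 3.1), and Section 7.1.8 makes passing this rule a condition for a phase III trial. If the schedule sentence is followed, two withdrawals among the first five patients trigger nothing. If the boundary list is followed, they stop the study. Anyone approving the plan on the strength of the quoted probabilities needs to know which rule delivers them.

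**Working it through.** **Inputs**, all from Section 7.1.7 except the sample size of 30 (Section 7.1.1): the two candidate look schedules, the six boundaries, the 15% threshold with its one-sided 80% limit, and the six quoted probabilities.

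**Step 1. Are the boundaries right?** The exact lower limit L for k withdrawals in n patients solves P(X ≥ k | n, L) = 0.20. For 2/5, 3/10, 4/15, 5/20, 6/25 and 7/30, L is .169, .158, .157, .158, .160 and .162. Each exceeds .15, and each k is the smallest count for which this is so. The boundaries follow from the criterion.

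**Step 2. Method for the stopping probabilities.** Let f(x) be the probability of x withdrawals at a look without having stopped earlier. The probability of stopping at that look is the sum of f(x) over x at or above the boundary. The remaining f(x) is carried forward and convolved with the binomial distribution for the next group of patients.

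**Step 3. Reproduce the plan's figures with looks every five.** For a true rate of 30%:

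- Look at 5: 1 − .7⁵ − 5(.3)(.7⁴) = 1 − .1681 − .3602 = .4718.
- Look at 10, stopping at 3 in total: .1681 × P(Y ≥ 3) + .3602 × P(Y ≥ 2), with Y binomial(5, .3). This is .1681 × .1631 + .3602 × .4718 = .1973.
- Look at 15, by the same step: .1063.
- By 15: .4718 + .1973 + .1063 = .7754. The plan says .78.
- Looks at 20, 25 and 30 add .0647, .0424 and .0291, giving .9116. The plan says .91.

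**Step 4. Repeat with looks at 10, 20 and 30.** At 30%, the look at 10 gives 1 − (.0282 + .1211 + .2335) = .6172. Nothing more can happen by patient 15. The looks at 20 and 30 add .1908 and .0840, giving .8920.

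Cumulative probability of stopping, by 15 / by 30 patients:

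| True rate | Plan | Looks every 5 | Looks every 10 |
|---|---|---|---|
| 5% | .03 / .03 | .0298 / .0307 | .0115 / .0129 |
| 10% | .13 / .15 | .1290 / .1463 | .0702 / .0965 |
| 15% | not given | .2862 / .3535 | .1798 / .2852 |
| 20% | not given | .4673 / .5935 | .3222 / .5324 |
| 30% | .78 / .91 | .7754 / .9116 | .6172 / .8920 |

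A simulation of 500,000 trials per rate at 5%, 10% and 30% agrees with the exact values.

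**Step 5. Could another schedule explain the plan's figures?** None of those tried does. Looks every five starting at 10 give .014/.015, .089/.109 and .748/.903. Looks at 15 and 30 only give .006/.006, .056/.067 and .703/.876. A look after every patient gives .069/.071, .187/.207 and .799/.925. Requiring the boundary to be exceeded rather than reached, with looks every five, gives .530/.787 at 30%.

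**Step 6. Expected number of patients evaluated at a true 30%.**

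- Every five: 5(.4718) + 10(.1973) + 15(.1063) + 20(.0647) + 25(.0424) + 30(.1175) = 11.8.
- Every ten: 10(.6172) + 20(.1908) + 30(.1920) = 15.7.

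**Step 7. Enrolment lag.** Evaluation takes four months and enrolment is not held. At the 1–1.5 patients per month in Section 7.1.1, 4–6 more patients are on study when a look's data mature. The first look then comes with 9–11 enrolled (looks every five) or 14–16 (every ten).

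**The case against.** The contradiction is not disputable, but several points limit it.

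- **The plan's arithmetic is correct.** The boundaries and probabilities agree with each other and conflict only with the look-frequency sentence. This stands: the defect is an inconsistency, not a miscalculation.
- **A lenient reading exists.** Every ten could be the scheduled review, with the boundaries applying whenever they are reached. The text neither says this nor excludes it, so the boundaries at 5, 15 and 25 go unchecked only if the schedule sentence is taken literally. That ambiguity is itself a fault in a stopping rule.
- **Looks every ten are not worse in every respect.** Detection by 30 patients at a true 30% differs by about two points, and false stopping at 5% and 10% is lower. This stands, and confines the harm mainly to early detection.
- **The enrolment lag exists under either schedule.** It adds a similar number of patients to both. The target of 30 patients in 2–3 years also implies a slower 0.83–1.25 per month, hence a lag of 3.3–5 patients. This stands: the lag worsens the consequence of a late first look but is not caused by the inconsistency.
- **The intended schedule is not stated.** The boundaries, the probabilities and the description of monitoring as semi-continuous point to every five. The reference to the tenth patient in the enrolment sentence points the other way.

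**Conclusion.** The point holds. The stopping probabilities in Section 7.1.7 are those of a rule with looks every five patients, while the sentence that sets the schedule says every ten. No other section reconciles them.

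Taken literally, the schedule gives .62 rather than .78 for stopping by patient 15 at a true 30% rate, and about four more patients evaluated on average (15.7 − 11.8 = 3.9). At a true 20%, stopping by 30 patients falls from .59 to .53. At 10% it falls from .15 to .10, and at 5% from .03 to .01. The 30-patient figure at a true 30% hardly moves.

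These values assume independent withdrawals at a constant rate and stopping when a boundary is reached. They count evaluated patients only. Because this rule governs the primary endpoint and two careful readers could act differently on the same data, it must be corrected.

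**What to change.** Reconcile the schedule with the boundaries and probabilities in one of two ways.

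1. **Looks every five.** State in Section 7.1.7 that the withdrawal rate is assessed after every five patients become evaluable, and bring the following sentence about the tenth patient into line. All six boundaries and all six probabilities then stand unchanged. The cost is a small wording change and three extra tabulations of data already collected. False stopping at a true 10% is .15 rather than .10, which is the figure the plan already accepts.
2. **Looks every ten.** Delete the boundaries 2/5, 4/15 and 6/25 and the figures quoted after 15 patients. Restate the 30-patient probabilities as about .01, .10 and .89 for true rates of 5%, 10% and 30%. The cost is slower detection of a toxic regimen, as shown above.

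Under either option, say whether the count at each look is of patients treated or of patients who have become evaluable over the four months. The paragraph currently uses both terms.

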7.1.8 Interim Analysis

An interim analysis at 15 treated patients will be conducted to assess feasibility for maintenance therapy. If > 50% of patients are unable to receive > 50% of planned therapy in first 12 months of treatment, the study will be terminated due to lack of feasibility.

If this study regimen is deemed to be potentially efficacious and is not regarded as too toxic per stopping rules outlined above and observed EFS rate are consistent with rates that match or exceed historical benchmarks, then a phase III trial to show efficacy rate of this regimen over single agent therapy will be designed.

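### Section 7.1.7 words its toxicity looks as every ten patients, but its printed stopping probabilities need looks every five; and its slight downward bias is 4 to 5 points at the 20% rate it uses next

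*Combined protocol and SAP*

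**What the plan says.** Section 7.1.7 takes withdrawal for toxicity in the first four months as the safety measure: "A true withdrawal rate within first 4 months of 15% will be considered excessive". On timing it says "Withdrawal rate will be assessed after every ten patients are treated". On boundaries it says "Operationally observed rates that say regimen is too toxic would be 2/5, 3/10, 4/15, 5/20, 6/25 and 7/30". It then gives the probability of calling the regimen too toxic by 15 and by 30 patients: about .03 and .03 at a true rate of 5%, .13 and .15 at 10%, and .78 and .91 at 30%.

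On estimation it says that "the estimate of this rate, should the study run to completion, will be biased slightly downward". No size is given, and no range of true rates. The next sentence sets the bias aside and quotes 80% confidence of being within about .094 of the truth, "under the assumption that the true rate is 20" per cent.

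Section 7.1.8 (Interim Analysis) makes a phase III trial conditional, among other things, on a regimen that "is not regarded as too toxic per stopping rules outlined above".

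**The concern.** Two statements in one section do not fit the section's own figures.

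The first is the look schedule. Someone running the trial from the sentence on timing would look at 10, 20 and 30 patients and never apply the boundaries at 5, 15 and 25. The trial would then not have the printed stopping probabilities. The main loss is early detection of a high withdrawal rate.

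The second is the bias. A trial reaches 30 patients only by staying below every earlier boundary, so its raw proportion is a selected value. The plan gives the right direction, but a reader going straight on to the 20% precision statement will assume that the bias is slight there too. Toxicity is the only primary endpoint, and this sentence describes its estimate.

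**Working it through.** **Inputs, all from section 7.1.7.** Boundaries 2/5, 3/10, 4/15, 5/20, 6/25 and 7/30, stopping when the count is reached; six printed probabilities; precision .094 at 20% with n = 30.

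**Method.** Exact binomial path enumeration. Between looks, add Binomial(k, p) events for the k new patients. At each look, remove the paths at or above the boundary. The removed mass is the probability of stopping there.

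**Step 1: the printed probabilities.** At p = .30 with looks every five:
- stop at 5: 1 - .7^5 - 5(.3)(.7^4) = 1 - .1681 - .3602 = .4718 (unrounded terms)
- the recursion then gives .1973 at 10 and .1063 at 15, so by 15: .4718 + .1973 + .1063 = .7754
- adding .0647, .0424 and .0291 at 20, 25 and 30 gives .9116

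With looks every ten, only the look at 10 falls by patient 15: 1 - .7^10 - 10(.3)(.7^9) - 45(.09)(.7^8) = 1 - .0282 - .1211 - .2335 = .617. Adding .1908 at 20 and .0840 at 30 gives .892.

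| True rate | Plan, by 15 / 30 | Looks every 5 | Looks every 10 |
|---|---|---|---|
| 5% | .03 / .03 | .030 / .031 | .012 / .013 |
| 10% | .13 / .15 | .129 / .146 | .070 / .096 |
| 30% | .78 / .91 | .775 / .912 | .617 / .892 |

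Only looks every five return the plan's figures.

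**Step 2: the precision figure.** 1.2816 × sqrt(.2 × .8 / 30) = .0936, which is the plan's .094.

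**Step 3: bias given completion.** Bias = E[X/30 | no boundary crossed before patient 30] - p, from the same enumeration.

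| True rate | Bias in points, every 5 / every 10 | Probability of completing |
|---|---|---|
| 5% | -0.2 / -0.1 | .97 / .99 |
| 10% | -1.1 / -0.8 | .86 / .91 |
| 15% | -2.8 / -2.2 | .66 / .75 |
| 20% | -5.3 / -4.1 | .44 / .54 |
| 30% | -11.5 / -9.2 | .12 / .19 |

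At 20% the mean completed-trial estimate is 14.7% or 15.9%. Relative to .094 the bias is 5.3/9.4 = 56% or 4.1/9.4 = 44%.

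**Step 4: total error at 20%.** Selection also narrows the spread. RMSE = sqrt(bias² + SD²):
- every five: sqrt(.0527² + .0492²) = .072
- every ten: sqrt(.0414² + .0547²) = .069
- unmonitored n = 30: sqrt(.16/30) = .073

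The 80% exact (Clopper-Pearson) interval covers .901 or .917 of completed trials, against .895 unmonitored.

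**Step 5: late information.** The plan says "Enrollment will not be held though until the 10th patient enrolled becomes evaluable" and "Expect to enroll 1-1.5 patients per month". With a four-month window, 4 × 1 to 4 × 1.5 = 4 to 6 patients enter while the 25th is being evaluated, so the look at 25 may come too late. Dropping it from the every-five schedule changes the 20% bias from -5.3 to -4.5 points.

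**The case against.** The strongest reply is that the plan already discloses the bias, gives its direction correctly, confines it to completed trials and sets it aside before quoting .094. It never says that the bias is slight at 20%; that comes from reading two adjacent sentences together. At 5% and 10%, where completion is most likely, the adverb is fair. All of this stands, and it makes the second half of the point one of missing quantification rather than a wrong number.

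A reader might infer something stronger: that monitoring makes a misleadingly low result more likely. At a true 20%, 51% of completed trials (looks every five) or 44% (every ten) would report below 15%, that is 4/30 or fewer, against 25.5% of unmonitored trials. That comparison mixes denominators. As a share of all trials the figures are .438 × .512 = 22% and .545 × .441 = 24%, against 25.5%. Monitoring only removes paths, so it cannot raise this share.

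A reader might also infer that a regimen could wrongly pass because its estimate falls near 15%. The documents do not support that. The 15% limit is on the true rate, the criterion for the observed rate at 30 patients is 7/30 (23%), and section 7.1.8 refers to the stopping rules, not to the point estimate.

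None of this answers the look schedule, where the wording and the printed probabilities cannot both hold.

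**Conclusion.** Wrong as written, minor, with high confidence. The timing sentence does not deliver the printed probabilities. The largest gap is at a true 30% by 15 patients, .62 against .78; by 30 patients it narrows to .89 against .91. Looks every ten also lower the chance of stopping at a true 10%, from .15 to .10 by 30 patients, so the two schedules trade early detection against false alarms. The documents must say which one applies.

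The bias description holds at 5% and 10% but not at 20%, where it is -5.3 or -4.1 points. The size boundaries, sample size and .094 are not in question, and no stopping or phase III decision turns on the bias.

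The figures assume independent patients with a common rate, stopping when a boundary count is reached, and full evaluability at each look. Completion means reaching patient 30. If it also required staying below 7/30, the 20% bias would be -6.0 or -5.6 points. Stopping only when a boundary is exceeded would give -3.2 or -2.4, but that reading does not reproduce the plan's probabilities.

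**What to change.** 1. Reconcile the look schedule. Either state that withdrawal is assessed after every five patients, which matches the boundaries and probabilities already printed, or keep every ten, drop the unused boundaries and restate the probabilities as .012/.013, .070/.096 and .617/.892.
2. Replace the adverb with the bias and completion probabilities from step 3 for the chosen schedule.
3. State the limits beside it: the bias plays no part in the stopping or phase III decision, and at 20% RMSE and 80% interval coverage are no worse than without monitoring. If the share of trials reporting below 15% is cited, give the conditional and unconditional figures together.
4. Optionally, name in advance an exact interval to report with the raw proportion. This does not correct the bias, and among completed trials its 80% coverage falls to .66 or .74 at a true 25% and to .52 or .67 at 30% (every five / every ten).

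The cost is a few lines of text and a small exact calculation. Boundary values and sample size stay as they are. Stating looks every five commits the team to six assessments where the present sentence implies three. The plan would also say openly that a completed trial tends to under-report higher withdrawal rates.
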